### 1.1 Trial design

A randomized, double-blind, multicentre, parallel, placebo-controlled phase 2b study in subjects with idiopathic pulmonary fibrosis (IPF). All subjects enrolled into the study should have a diagnosis of IPF established within the previous five years, and a diagnostic HRCT scan assessed by central independent radiologists according to the ATS/ERS/Fleischner criteria available within the previous 12 months prior to screening.

The original design consisted of 3 treatment groups, placebo, GB0139 3mg and GB0139 10mg, with patients randomized in a 1:1:1 ratio. Stratification in the original version of the study was according to the patient's standard of care treatment at enrollment;

- SoC1 being patients currently treated with either pirfenidone or nintedanib,
- SoC2 being patients not currently treated with pirfenidone or nintedanib.

A subject's SoC must have been deemed as stable by the Principal Investigator or treating physician before their enrollment in the study.

It was initially planned to randomize approximately 450 patients to this design across approximately 70 sites from the European Union and 30 sites from the United States. This design was intended to evaluate the efficacy and safety of GB0139 over 52 weeks of dosing in addition to the subject's current standard of care (SoC) (including treatment with either pirfenidone or nintedanib). It was planned to continue blinded treatment beyond week 52 and up to week 104 to provide further safety follow-up information.

Following a review of unblinded efficacy and safety data by the study's DSMB in February 2021, the study design has been modified based on the DSMB's recommendation. Participants randomized to the 10mg GB0139 group, and all those taking nintedanib or pirfenidone, have been discontinued from the study. In addition, subjects who had already

	Plus-Project Statistical Analysis Plan	
	Protocol Number: GALACTIC-1	Version: 1

completed 52 weeks of treatment were discontinued. In total, about 320 subjects had been randomized under the original design, and approximately 200 were discontinued.

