In the revised version of the study, post the changes following the DSMB recommendations, participants who are not taking nintedanib or pirfenidone at screening and during the study continue in the study. New patients are recruited and randomized to receive either 3mg GB0139 or placebo in a 2:1 ratio, to ensure the same proportion of patients on active drug as in the original design. Approximately 141 patients are expected to be enrolled into the modified design. Both nintedanib and pirfenidone are prohibited in the revised version of the study.

The revised study design consists of a screening period up to 6 weeks, a 52-week double-blind treatment period and a safety follow-up call 7 days post last visit. The duration of the entire trial for each subject will be approximately 59 weeks from first screening to the final safety follow up.

[figure not shown]
After giving Informed Consent, the subject may be selected for the study at Visit 1. Subjects who fail screening may be permitted to undergo re-screening one additional time. If they are successfully re-screened then they will be allocated a new unique subject ID number. If all exclusion and inclusion criteria are fulfilled then randomization occurs at Visit 2 (Week 0). Further visits are scheduled at Week 4 (V3), Week 8 (V4), Week 12 (V5), Week 26 (V6), Week 40 (V7), and Week 52 (V8). Visits 3, 4 and 5 should occur within  $\pm 3$  days of the scheduled time point. Visits 6 and 7 should occur within  $\pm 7$  days of the scheduled time point.

Details for the data collected at each visit are given in the time and events table in Section 11.2.

The revised design is shown in Figure 1 below. For reference, the original design is shown in Section 11.1.

	Plus-Project Statistical Analysis Plan	
	Protocol Number: GALACTIC-1	Version: 1

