## 1.3 Study Populations

There are 3 populations of interest. These are as follows:

[figure not shown]
- **Primary Population** : Subjects recruited under the new design, plus those from the original design recruited to SoC2 (not being treated with nintedanib or pirfenidone prior to screening) and randomized to either placebo or 3mg GB0139.
- **SoC1 Population/Combination**: Subjects recruited under the original design to SoC1 (current treatment at baseline with nintedanib or pirfenidone).
- **SoC2 Population/Monotherapy**: Those subjects from the original design in the SoC2 stratum (not receiving nintedanib or pirfenidone at baseline), plus all subjects from

	Plus-Project Statistical Analysis Plan	
	Protocol Number: GALACTIC-1	Version: 1

the new design. SOC2/Monotherapy Population is the Primary Population plus SoC2 10 mg.

These populations are described visually in Figure 2 below.

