### 3.2 Randomization and Blinding

In the original design, within each SoC subpopulation (SoC1: subjects on nintedanib/pirfenidone at baseline, SoC2: subjects not treated with nintedanib/pirfenidone), subjects were randomized in blocks to double-blind treatment in a 1:1:1 ratio (GB0139 3 mg: GB0139 10 mg: Placebo).

For the updated design, there is no stratification and subjects are randomized in a 2:1 ratio GB0139 3mg: Placebo. The unbalanced randomization is to maintain the same probability of allocation to placebo post design change, since it is considered that this may facilitate participant enrollment.

The Sponsor arranged for the randomization and the packaging and labelling of trial medication. The randomization list will be generated using a validated system, which involves a pseudo-random number generator so that the resulting treatment will be both

	Plus-Project Statistical Analysis Plan	
	Protocol Number: GALACTIC-1	Version: 1

reproducible and non-predictable. The block size will be documented in the Clinical Study Report (CSR). Access to the codes will be controlled and documented.

This study is a double-blind study which will be maintained throughout the study, including the follow up period. The only exception to this is at the point of the design change, when the 10mg group in the SoC2 stratum had to be unblinded in order to withdraw them from the study early. Study medication is identified by a medication code number. Packaging and labelling will be otherwise identical. An Integrated Web Response System (IWRS) will be used to assign subjects to treatment groups at study start. The randomization code will be kept undisclosed up to database lock.

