- All deaths (Note: time to death is limited to a follow-up period of Day 379)

	Plus-Project Statistical Analysis Plan	
	Protocol Number: GALACTIC-1	Version: 1

Further summaries by SOC and PT will be produced for all TEAEs, TEAEs by SoC, PT and maximum severity, treatment related TEAEs, serious TEAEs, TEAEs leading to treatment discontinuation and TEAEs leading to death. These will be presented by SOC and PT, sorted by decreasing frequency overall and then alphabetically. An additional summary all AEs post follow-up (i.e. post treatment end date + 14) will be produced by SOC and PT.

Additional summaries of all TEAEs and of serious TEAEs by PT only, sorted by decreasing frequency overall, will be presented.

Summaries of COVID related (per eCRF) TEAEs and serious COVID related TEAEs will also be produced. In addition, summaries of TEAEs and Serious TEAEs related to IPF exacerbations (i.e. those events marked on the eCRF as related to IPF exacerbation) will be provided.

Serious TEAEs and TEAEs leading to discontinuation of study drug will be presented separately for the SoC1 / Combination and SoC2 / Monotherapy Populations.

Additionally, the incidence of by time period (0 - 13 weeks, >13 weeks – 26 weeks, >26 weeks - 39 weeks, >39 weeks – 52 weeks, ≥ 52 weeks) will be presented. The presentation will include all TEAEs, serious TEAEs, TEAEs leading to treatment discontinuation, and TEAEs leading to death. The denominator for each period will be the number of subjects on treatment at the beginning of that time period. This summary will be repeated for the SoC1 / Combination and SoC2 / Monotherapy Populations.

Each TEAE event rate (per 100 patient years) will also be summarised by preferred term within each system organ class. For each preferred term, the event rate will be presented and will be defined as the number of patients with that AE divided by the sum of the duration from the start of treatment to 14 days after the last treatment dose (for patients without the event) and the time to the AE (for patients with the event) in each group multiplied by 100. This will also be repeated for serious TEAEs.

Risk differences for proportion of subjects with the following TEAEs (with associated 95% confidence intervals) comparing GB0139 groups to Placebo will be estimated:-

- TEAE
- TEAE by maximum severity (overall and within related TEAEs)
- TEAE by maximum relationship to study drug (overall and within serious TEAEs)
- Serious TEAE

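### In the SoC2/Monotherapy safety tables, crude serious-TEAE and discontinuation-TEAE percentages set 10 mg against arms with a different observation time and a partly later recruitment

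*SAP*

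**What the plan says.** **Who is in the table.** SAP 1.3 defines the population: "SOC2/Monotherapy Population is the Primary Population plus SoC2 10 mg". SAP Table 2 gives it three treatment columns: placebo, 3 mg and 10 mg.

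**Who stopped.** SAP 1.1 says of the 2021 change: "Participants randomized to the 10mg GB0139 group, and all those taking nintedanib or pirfenidone, have been discontinued from the study". It adds that those who had already "completed 52 weeks of treatment were discontinued", with no restriction by arm. SAP 3.2 confirms the point for this stratum. The one exception to blinding came at the design change, "when the 10mg group in the SoC2 stratum had to be unblinded in order to withdraw them from the study early".

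**Who continued.** Under SAP 1.1, subjects not on nintedanib or pirfenidone stay in the study. New subjects are randomized to 3 mg or placebo only, with "a 52-week double-blind treatment period and a safety follow-up call 7 days post last visit". Before the change, treatment could run longer: "It was planned to continue blinded treatment beyond week 52 and up to week 104 to provide further safety follow-up information".

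**What is tabulated.** In SAP 7.3.2 the TEAE window closes 14 days after the last dose, and the basic summary is the number and percentage of subjects with an event. For the two additional populations, "Serious TEAEs and TEAEs leading to discontinuation of study drug will be presented separately for the SoC1 / Combination and SoC2 / Monotherapy Populations". Risk differences in proportions "comparing GB0139 groups to Placebo will be estimated", with no population named. SAP 5.2 puts all collected safety data into the summaries, so these tables have no common cut date. SAP 7.2.4.6 also gives AE and SAE percentages for each population, limited to onsets before Day 379. That caps long follow-up but does not equalise short follow-up.

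**What adjusts for time.** SAP 7.3.2 has a table by 13-week period, whose denominator is subjects on treatment at the start of the period; it is explicitly repeated for SoC2. It also defines a rate per 100 patient-years by preferred term, repeated for serious TEAEs. No sentence extends that rate to SoC2, and SAP 7.3 covers the additional populations only where an individual section says so.

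**The concern.** A percentage of subjects with at least one event rises with time observed. Within SoC2 the 10 mg window was closed by the design change, while the placebo and 3 mg windows mostly were not. With the same underlying event rate in every arm, the 10 mg column would then tend to show a smaller percentage.

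There is a second, separate difference. Placebo and 3 mg include subjects recruited after the change and 10 mg does not, so part of the comparison is non-concurrent. Adjusting for exposure does not remove that.

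What is at stake is the safety description of the dose that was withdrawn on the DSMB's recommendation. A real excess of serious events at 10 mg could be understated or hidden in the table where a reader would look for it.

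**Working it through.** The documents give no serious-event rate, accrual curve, SoC2 10 mg sample size or SoC2 10 mg exposure. There is no plan figure on this point to reproduce, and the sizes below rest on stated assumptions.

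**1. Model.** Constant event hazard λ, equal in all arms, 0.15 to 0.30 per year. Accrual is uniform over A years before the stop, so time from randomization to the stop is u ~ U(0, A). Exposure in years:
- 10 mg: u, capped at 2 (Week 104).
- Original-design placebo: the larger of 1 and u, capped at 2.
- New-design placebo: 1.

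Original-design subjects make up 30% to 60% of placebo. There is no dropout. The tail is 14/365.25 = 0.0383 year. The crude percentage is the mean of 1 − exp(−λ × (exposure + 0.0383)).

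**2. Worked case, A = 1.** Every original placebo subject has 1 year of exposure.
- λ = 0.15: placebo 1 − exp(−0.15 × 1.0383) = 14.4%. 10 mg 1 − exp(−0.15 × 0.0383) × (1 − exp(−0.15))/0.15 = 1 − 0.9943 × 0.9286 = 7.7%.
- λ = 0.30: placebo 1 − exp(−0.30 × 1.0383) = 26.8%. 10 mg 1 − 0.9886 × 0.8639 = 14.6%.

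**3. Range over A** (same formulas; low and high ends over λ and the placebo mix). The last column is the true 10 mg hazard ratio at which the two crude percentages would be equal.

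| A (years) | 10 mg reaching 1 year | 10 mg % | Placebo % | 10 mg minus placebo (points) | Hazard ratio hidden |
|---|---|---|---|---|---|
| 1 | none | 7.7 to 14.6 | 14.4 to 26.8 | −6.8 to −12.2 | about 2.0 |
| 1.5 | one third | 11.0 to 20.4 | 14.7 to 27.8 | −3.8 to −7.4 | about 1.4 |
| 2 | one half | 14.1 to 25.7 | 15.3 to 29.8 | −1.2 to −4.1 | 1.1 to 1.2 |
| 2.25 | 56% | 15.5 to 27.9 | 15.6 to 30.7 | −0.2 to −2.8 | 1.0 to 1.1 |
| 2.5 | 60% | 16.6 to 29.7 | 15.9 to 31.4 | +0.7 to −1.8 | 0.95 to 1.1 |

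The reversal at 2.5 years appears when only 30% of placebo is from the original design (0.6 to 0.7 points). Early 10 mg subjects then run past Week 52, while most placebo subjects stop there.

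**4. A second set of assumptions.** Take 10 to 40 events per 100 patient-years, with the other arms observed for 52 weeks plus 14 days (9.8% to 33.9%). If half of 10 mg completed 52 weeks and the rest stopped uniformly before that, 10 mg reads 2.3 to 7.6 points low. If all stopped at Week 26, it reads 4.6 to 14.6 points low.

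**5. Does the by-period table remove it?** At 30 per 100 patient-years, a full 13-week period carries a risk of 1 − exp(−0.30 × 13/52.18) = 7.2%. With stopping uniform over 52 weeks and no tail, 10 mg shows 6.3%, 6.0%, 5.4% and 3.7% in the four periods, because a subject stopped mid-period stays in the denominator. The remaining gap is 0.9 to 3.5 points per period.

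**6. Does the patient-year rate remove it?** As the SAP defines it, expected events per subject are 1 − exp(−λt) and expected time at risk is (1 − exp(−λt))/λ. Their ratio is λ at any t, so the rate is 30.0 per 100 patient-years whether t is 28 weeks or 54 weeks. The exposure artefact goes if the hazard is constant. The non-concurrency stays.

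**The case against.** The strongest reply is that the SAP already shows the imbalance and partly handles it. The by-period table covers serious, discontinuation and fatal TEAEs and is repeated for SoC2. Exposure (SAP 7.3.1) and time to premature discontinuation (SAP 7.3.8) are also repeated for this population. Safety is descriptive without hypothesis tests, and the primary safety assessment concerns 3 mg and placebo (protocol 14.5.2). All of this stands and limits the consequence. It does not correct the percentages: step 5 shows what the by-period table leaves, and the exposure summaries only disclose the difference.

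Several stronger readings are tempting, and the documents do not support them:
- *10 mg must look safer by construction.* Treatment could run to Week 104, so early 10 mg subjects may have passed Week 52 before the stop. Direction and size depend on accrual, and step 3 includes a reversal. A large true excess would also still show: with all 10 mg stopping uniformly over 52 weeks, a hazard ratio of 2.5 puts 10 mg 2.5 to 5.2 points above placebo.
- *All other subjects ran to Week 52.* Subjects taking nintedanib or pirfenidone were also discontinued, which may include SoC2 subjects who had started one, and ordinary dropout occurs. Adding dropout of 20% to 40% per year at A = 1 lowers the gap from 6.8–12.2 to 5.2–10.7 points.
- *Crude 10 mg risk differences are definitely planned.* Only the plural for the GB0139 groups suggests it. The default-to-Primary rule that keeps the patient-year rates out of SoC2 would keep these out too.
- *SoC1 has the same fault.* Its arms stopped together, so this differential truncation does not arise there.
- *The mandated stop inflates TEAEs leading to discontinuation.* A sponsor stop is not an adverse event, and protocol 10.5 lists it as a separate reason.

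**Conclusion.** The concern holds in a limited form. The crude serious-TEAE and discontinuation-TEAE percentages for SoC2/Monotherapy compare arms with unequal observation time and a partly non-concurrent control. The bias most likely favours 10 mg.

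Its size is not determined by the documents. With equal constant hazards of 0.15 to 0.30 per year, uniform accrual and no dropout, it is about 7 to 12 points at one year of accrual and 1 to 4 points at two years. From about 2.25 years it can be near zero or reversed. The adjustment that would remove the exposure part is already defined in the SAP, but only by preferred term and without a stated repeat for this population.

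No confirmatory conclusion depends on these tables. This is a cheap improvement to a descriptive comparison, and it goes further than asking for missing detail because the tables as written would carry the bias.

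**What to change.** In SAP 7.3.2:

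1. Repeat the per-100-patient-year rates for the SoC2/Monotherapy population. Add an overall rate for any serious TEAE and for any TEAE leading to discontinuation, and use these rates for 10 mg against placebo.
2. Add one table limited to original-design SoC2 subjects, with all arms cut at the design-change date and the same 14-day tail counted in each. Within the stratum these subjects were randomized 1:1:1 over the same period, so the cut equalises potential follow-up and removes the non-concurrent controls. It does not rely on a constant hazard.
3. State whether risk differences are produced for 10 mg. If they are, compute them only on the cut data.

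The cost is a few sentences of SAP wording before database lock and a small number of re-run tables using an existing derivation. The downside is fewer placebo and 3 mg events in the cut table, and so wider intervals. The uncut tables can stay as descriptive output.

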### **7.3.2 Adverse Events**

Adverse events (AEs) from the 'Adverse Events' eCRF will be coded for summarization using the most recent upversioned MedDRA coding as specified in the DMP. In the event that no

	Plus-Project Statistical Analysis Plan	
	Protocol Number: GALACTIC-1	Version: 1

coding information is available for a specific AE, the AE will be presented as an “Uncoded” in summary tables.

A Treatment Emergent AE (TEAE) is defined as any protocol defined AE (collected as a unique record from the AE eCRF page) with an onset between the date of first dispensing of study drug (from the ‘Treatment Compliance’ eCRF forms) and date of last dose recorded + 14 days inclusive (date of last dose from the ‘Disposition Study Completion’ eCRF). If the date of onset is the same as the date of first dispensing of study drug, then the recorded start of event relative to first dose from the eCRF (before/after) will be used to classify the AE as either a TEAE (after) or a non-TEAE (before).

Missing and/or incomplete dates/times for AEs will not be imputed. For partial/missing dates:

- If the start or stop month/year (if day is missing) or year (if day and month are missing) of the AE is prior to the respective month/year or year of the first dose of study drug, then the AE will be classed as a Non-TEAE.
- If the start month/year (if day is missing) or year (if day and month are missing) of the AE is after the respective month/year or year of the last dose of study drug + 30 days, then the AE will be classed as a Non-TEAE.
- Otherwise, the AE will be classed as a TEAE.

For TEAE summaries presenting the incidence frequency and percentage, the number of actual unique TEAEs (meeting each criteria) will also be presented. For incidence summaries, a subject with multiple TEAEs will contribute only once to the count for a given summary and the maximum severity and relationship will always be used. The number of unique TEAEs will always be presented as per the severity and relationship for the unique TEAEs. Missing relationship will be considered related to study drug and missing severity will be considered severe.

The number and percentage of subjects reporting at least one of the following will be summarized:

- TEAE
- TEAE by maximum severity (overall and within related TEAEs)
- TEAE by maximum relationship to study drug (overall and within serious TEAEs)
- Serious TEAE
- TEAE leading to treatment discontinuation
- TEAE leading to death

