### 7.3.8 Time to Premature Treatment Discontinuation

The date of premature treatment discontinuation will be derived from the ‘Disposition Study Completion’ eCRF.

	Plus-Project Statistical Analysis Plan	
	Protocol Number: GALACTIC-1	Version: 1

The time to premature treatment discontinuation (i.e. prior to Day 358, Week 52 – 1 week) in weeks will be derived as (date of treatment discontinuation – date of randomization +1)/7.

If a subject does not prematurely discontinue treatment prior to Day 358, they will be censored in the analysis at Day 359.

Summary tables of the time to premature treatment discontinuation by treatment group (as a continuous variable for those that prematurely discontinued), as well as Kaplan Meier plots by treatment will be produced. These summaries and plots will be repeated for all populations.

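### The AE-by-period table can overstate the Week 52-and-later row, because its numerator runs to 14 days after last dose and its denominator counts only subjects still on treatment

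*SAP*

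**What the plan says.** SAP 7.3.2 sets three rules for this table.

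- **Numerator window.** A TEAE has its onset between first dispensing and "date of last dose recorded + 14 days inclusive".
- **Numerator content.** "The presentation will include all TEAEs, serious TEAEs, TEAEs leading to treatment discontinuation, and TEAEs leading to death". Nothing limits these events to subjects who are in the row's denominator.
- **Denominator.** "The denominator for each period will be the number of subjects on treatment at the beginning of that time period".

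The last two rows are ">39 weeks – 52 weeks, ≥ 52 weeks", so Week 52 itself belongs to both. The exposure categories in SAP 7.3.1 end with >52 weeks and do not overlap at that point.

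The revised design has "a 52-week double-blind treatment period and a safety follow-up call 7 days post last visit" (SAP 1.1). The schedules in Protocol 2.2 and SAP 11.2 put the Week 52 visit at Day 365 ±7. SAP 7.3.8 treats stopping as premature only if it is "prior to Day 358, Week 52 – 1 week", so a last dose on Days 358 to 364 is ordinary completion.

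The patient-year rate in the same section handles follow-up differently. For subjects without the event it sums "the sum of the duration from the start of treatment to 14 days after the last treatment dose", which agrees with the TEAE window.

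**The concern.** A percentage of subjects with an event is interpretable only if everyone who can enter the numerator is also in the denominator. Here a subject whose last dose falls up to 14 days before a boundary can add a TEAE to the next row without being counted in its divisor.

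At most boundaries few subjects are in that position. At Week 52 the row opens just as planned treatment ends, so a large share of completers may be.

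The table covers serious TEAEs and TEAEs leading to death, in a trial whose design was changed after the DSMB reviewed unblinded efficacy and safety data. An artificial rise in the last row could be read as late toxicity.

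**Working it through.** The documents give no figure for this table, so there is none to reproduce. The check counts days.

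**Notation.** L is the last-dose day and S is the first day of the last row. S is Day 365 on the visit schedule, or Day 364 if weeks are days divided by 7 (52 × 7 = 364). The planned denominator holds subjects with L ≥ S. The numerator can draw on subjects with L + 14 ≥ S. The inflation factor against a matched denominator is

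(number with L + 14 ≥ S) / (number with L ≥ S).

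**Assumption.** The documents do not give the distribution of L. The base case spreads it evenly over the visit window, Days 358 to 372 (15 days).

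**Base case, S = 365.** Days 365 to 372 are 8 of the 15 days, so 8/15 = 53% of completers are in the denominator. The earliest stopper has 358 + 14 = 372 ≥ 365, so all 15/15 can enter the numerator. The factor is 15/8 = 1.88. For example, with 100 completers of whom 10 have a TEAE in the row, the plan gives 10/53.3 = 18.8% and a matched denominator gives 10/100 = 10.0%.

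**Other assumptions for the last row.** The bell-shaped cases are truncated to Days 358 to 372, with S = 365.

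| Assumption | Share in denominator | Factor |
|---|---|---|
| Even spread, S = 364 | 9/15 | 1.67 |
| Even spread, last dose the day before the visit, S = 365 | 7/15 | 2.14 |
| Bell-shaped, centred on Day 365, SD 2 to 4 days | 0.60 to 0.55 | 1.67 to 1.81 |
| Bell-shaped, centred two days late, SD 2 to 4 days | 0.90 to 0.72 | 1.12 to 1.39 |
| Bell-shaped, centred two days early, SD 4 to 2 days | 0.38 to 0.225 | 2.63 to 4.45 |

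**Subjects treated past Week 52.** Of the original design SAP 1.1 says: "It was planned to continue blinded treatment beyond week 52 and up to week 104". The number still on drug at Week 52 and beyond is not given. If they form a share q of subjects at the boundary, the factor is 1/(q + (1 − q) × 8/15). This is 1/0.58 = 1.72 at q = 10% and 1/0.767 = 1.30 at q = 50%.

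**Restricting the numerator instead.** Suppose the row counted only events in subjects on treatment at S, and events occur in proportion to window days in the row, L + 14 − S + 1. With S = 365, all completers contribute 8 + 9 + … + 22 = 225 days, and those in the denominator contribute 15 + … + 22 = 148. The factor is 225/148 = 1.52. If AE capture ended 7 days after last dose, it would be 120/92 = 1.30.

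**Earlier rows.** Assume a share d discontinues evenly over 52 weeks. At boundary week b, the share on drug is 1 − d × b/52, and the share stopped within the previous 14 days is d × 14/364. The factor is the sum of the two divided by the first. For d = 10%, b = 13 it is (0.975 + 0.0038)/0.975 = 1.004. For d = 40%, b = 39 it is (0.70 + 0.0154)/0.70 = 1.022.

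**The case against.** Several counterarguments hold at least in part.

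- **The size is not in the documents.** A ±7-day visit window does not show that half the completers are off drug at the boundary. Protocol 8.1 supplies drug until the next visit plus one week, so late attenders can keep dosing. A reader might infer that the last row is simply doubled. The documents support only a range that depends on assumptions.
- **Completers do not contribute equally.** On the base case those missing from the denominator have 8 to 14 window days in the row, and those in it have 15 to 22. AE capture is itself inconsistent: the schedules collect AEs up to the phone call, 7 to 14 days after the last visit, while Protocol 11.3 says 30 days after last dose. Both points bear on the 1.52 and 1.30 figures.
- **The scope is narrow.** A reader might extend the problem to every row or to the SoC1 population. Earlier rows move by about 2% at most under the stated assumptions. The sponsor-mandated SoC1 stops fell at staggered study days, so the factor there should be near 1. TEAEs leading to discontinuation should also be little affected, since an event that starts after the last dose cannot have caused the stop.
- **Between-arm bias is unquantified.** A reader might infer a biased comparison, because 3 mg to placebo allocation was 1:1 in the original design and 2:1 afterwards, so placebo holds more original-design subjects proportionally. The distortion need not cancel between arms. But the documents do not say how many subjects in each arm were dosed past Week 52, so neither its size nor its importance can be established.

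One defence fails. On treatment might be read to include the 14 days, which would remove the mismatch. But the patient-year paragraph in the same section writes the 14 days out where they are meant, and SAP 7.3.9 lists on-treatment and post-treatment as separate periods.

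**Conclusion.** As written, the rule does not give a valid incidence proportion in the ≥52-week row for subjects whose treatment is planned to end at Week 52. With last doses spread evenly over Days 358 to 372 and the row opening on Day 365, the percentage is about 1.9 times the matched one. Depending on visit timing, AE capture and the share of original-design subjects still on drug, the factor is about 1.1 to 2.1. It goes higher only if visits run early. The Week 52 overlap between the last two rows is a separate, smaller defect that needs no assumption.

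The consequence is limited. The table is descriptive and the Protocol plans no safety hypothesis tests. The patient-year rates, overall incidences and risk differences do not use this denominator. What is at risk is the absolute level of one row and its comparison with the rows before it. That justifies a correction before database lock.

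**What to change.** In SAP 7.3.2, define the denominator for each period as subjects who, at the start of the period, are on treatment or within 14 days after their last dose. This matches the TEAE window and the patient-year table. Label the last row >52 weeks, as SAP 7.3.1 already does for exposure.

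Showing original-design subjects separately in the last row is optional. It would keep longer exposure apart from 14-day tails.

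The cost is one revised SAP sentence, one changed label and a small programming change. No new data are needed.

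The post-dose windows should be reconciled at the same time: 14 days in the SAP's TEAE definition, 30 days in its partial-date rule and 28 days in Protocol 14.5.2. The denominator should follow whichever window is kept.
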